3.2. Study rationale

The TRACII study has examined the safety, tolerability and efficacy of different Triple Artemisinin based Combination Therapies (TACTs) such as DHA-piperaquine+mefloquine (DHA-PPQ+MQ) and artemether-lumefantrine+amodiaquine (AL+AQ). The preliminary results of this study show that the TACT artemether-lumefantrine+amodiaquine is as effective and safe as the standard ACT artemether-lumefantrine, even in children recruited in the Democratic Republic of Congo. Further, the TACT DHA-PPQ+MQ was found to be highly efficacious at study sites in Cambodia, Thailand and Vietnam, even though the efficacy of the ACT DHA-PPQ was poor at these sites. However, in a study assessing the pharmacokinetics of the TACT DHA-PPQ+MQ in healthy volunteers, a significant drug-drug interaction was observed wherein the addition of MQ to the ACT DHA-PPQ significantly reduced the absorption of DHA ([name] et al.; manuscript in preparation). Similarly, a substantial reduction in the absorption of DHA was also observed in malaria patients included in the TRACII study though this did not affect parasite clearance half-lives. Taken together, these data indicate that there is an increased risk of sub-therapeutic exposure to DHA at its current dosage when co-administered with piperaquine and mefloquine as a TACT. Therefore, drug combinations wherein DHA (target dose of 2.4 mg/kg in the current fixed dose combination) is replaced with artesunate (target dose of 4 mg/kg), which is completely metabolised to DHA very rapidly after absorption [23], will be tested in this study as artesunate-mefloquine (ASMQ) with or without PPQ (ASMQ+PPQ) along with AL with or without AQ.

Co-blistered or co-formulated TACTs could be rapidly deployed in areas with multidrug resistant malaria. For other regions, the safety and efficacy of TACTs should be assessed in the local setting in order to guarantee rapid deployment in case resistance starts affecting treatment efficacy. Furthermore, deployment of TACTs on a wide scale could prevent or delay the emergence and spread of antimalarial resistance in areas where this has not yet happened. The efficacy, safety and tolerability of TACTs need extensive evaluation in adults and children before policy recommendations can change and widespread deployment can be considered.

Therefore, we aim to conduct a large scale randomized clinical trial in up to 8 African countries to compare the efficacy, safety and tolerability of the TACTs artemether-lumefantrine+amodiaquine and artesunate-mefloquine+piperaquine and the standard ACTs artemether-lumefantrine+placebo, and artesunate-mefloquine+placebo. Early signs of independent emergence of artemisinin resistance have recently been detected in Rwanda [24]. This implies that there may soon be an urgent need to deploy novel treatments such as the TACTs

being tested in this trial if the ACTs being used as first-line treatments start to fail in the country. High coverage of malaria control interventions across Rwanda which have led a steep reduction in the incidence of malaria across the country, including in the north-west where the artemisinin resistance was detected and also where this study will be conducted. Accordingly, to ensure that the target sample size is reached, this study will be conducted in Rwanda with only 2 arms. The TACT artemether-lumefantrine-amodiaquine will be compared with artemether-lumefantrine with respect to efficacy, safety and tolerability given that this TACT could be more readily deployed if needed to replace ACTs.

Given that the observations of low incidence of QTc prolongation are from a relatively small population, they need further monitoring and confirmation. Accordingly, in this study electrocardiograph measurements (ECGs) will also be performed at baseline and several time points thereafter to assess the effect of antimalarials on the QT/QTc interval.

In addition to the main clinical outcomes of the study, we aim to assess the extent of the spread or the de novo emergence of resistance to the antimalarials in the combinations through detailed in vivo and in vitro assessments and to study the pharmacokinetics and inter-drug interactions of the drugs, the parasite- and host-related factors affecting treatment outcomes. Finally, we aim to gain insights into the spread of resistance mediated by population movements and parasite gene flows in general through travel surveys and geographic localization of parasite genetic data.

4. OBJECTIVES

4.1. Primary objectives

To compare the efficacy of the matching ACTs and TACTs as defined by the 42-day PCR corrected adequate clinical and parasitological response (ACPR) within each individual site.

Matching comparisons of ACT and TACT are as follows:

- AL+PBO versus AL+AQ
- ASMQ+PBO versus ASMQ+PPQ

4.2. Secondary objectives

- To compare the safety and tolerability of ACTs and TACTs within and across sites and regions, including comparisons of 'non-matching' ACTs vs TACTs (AL+PBO versus ASMQ+PPQ, ASMQ+PBO versus AL+AQ).
- To compare additional measures of treatment efficacy between treatment arms, including the 63-day ACPR, the post-treatment prophylactic effect of ACTs and TACTs defined as the 42-day and 63-day PCR uncorrected ACPR, gametocyte carriage, parasite clearance rates and fever clearance.
- To assess pharmacokinetic and pharmacodynamic interactions between antimalarials in TACTs

4.3. Exploratory objectives

- To assess molecular genetic and transcriptomic correlates for artemisinin and partner drug resistance of the infecting *P. falciparum* strains and to assess their *ex vivo* and *in vitro* drug susceptibility.
- To compare the selective effect of ACTs versus TACTs on parasites carrying mutations associated with resistance to antimalarial drugs
- To obtain additional safety data (in particular incidence, rate and magnitude of haemolysis) on the deployment of single low dose primaquine, stratified according to G6PD status/genotype
- To obtain additional data on the effect of the host genotypes known to affect pharmacokinetics and pharmacodynamics of antimalarials
- To obtain data on the place of residence, work, recent travel history and mobile phone usage in order to improve the understanding of local malaria transmission by identifying behaviours and risk factors associated with malaria infection and possible routes of spread of malaria and artemisinin resistance
- To assess new methods for determination of gametocytaemia, parasite phenotypes and genotypes
- To assess the correlation between anti-*Plasmodium falciparum* antibodies and drug efficacy measures
- To assess the prevalence of parasites carrying complete or partial deletions in *pfhrp2* gene

5. PRIMARY, SECONDARY AND EXPLORATORY ENDPOINTS

5.1. Primary endpoint

42-day efficacy defined as PCR corrected adequate clinical and parasitological response (ACPR).

5.2. Secondary endpoints

- For safety and tolerability: Incidence of adverse events and serious adverse events within the first 42 days including markers of hepatic, renal or bone marrow toxicity; cardiotoxicity, in particular QT or QTc-interval above 500 ms at timepoint H4 and H52/H64 and between these time points; change in haemoglobin concentration at day 3, 7, 28, stratified for G6PD status/genotype; proportion of subjects requiring retreatment due to vomiting within 1 hour after administration of the study drugs; proportion of subjects that reports completing a full course of observed TACT or ACT without withdrawal of consent or exclusion from study because of drug related serious adverse event

- For efficacy: 63-day PCR corrected and uncorrected efficacy; 42-day PCR uncorrected efficacy; parasite clearance half-life assessed by microscopy as primary parameter to determine parasite clearance; proportion of subjects with microscopically detectable *P. falciparum* parasitaemia at Day 3; fever clearance time (i.e. the time taken for the tympanic temperature to fall below 37.5 °C in patients who were febrile at inclusion); proportion of subjects with gametocytaemia during and after treatment stratified by presence of gametocytes at enrolment.
- For PK/PD interactions: Pharmacokinetic profiles and interactions (including C_{max} and AUC) of artemisinin-derivatives and partner drugs in ACT and TACT treated subjects in correlation with pharmacodynamics measures of drug efficacy; day 7 plasma levels of partner drugs in correlation with treatment efficacy and treatment arm

5.3. Exploratory endpoints

- Comparison of 63-day vs 42-day PCR corrected and uncorrected efficacy of ACTs vs TACTs
- Proportions of recurrent infections with parasites carrying mutations of known functional significance
- Proportions of specimens collected at baseline with parasites carrying mutations of known functional or operational significance (*pfkelch13*, *pfprt*, *pfmdr1*, *pfdhfr*, *pfdhps*, *pfplasmepsin2*, partial or complete deletions of *pfhrp2* and other current parasite genetic markers associated with resistance or identified over the course of the study)
- Candidate markers of resistance identified through genome wide association studies with *in vivo* or *in vitro* parasite drug sensitivity phenotypes
- *In vitro* sensitivity of *P. falciparum* to artemisinins and partner drugs according to study sites and genotype
- Accuracy of SNPs assessment from dry blood spots versus from whole genome sequencing in leukocyte depleted blood samples
- Correlation between qPCR based versus microscopy based assessments of parasite clearance dynamics
- Correlation of parasite clearance metrics as assessed by microscopy versus digital microscopy
- Comparison of transcriptomic patterns of drug sensitive and resistant parasites before treatment and 6, 12 and 24 hours after start of treatment
- Levels of RNA transcription coding for male or female specific gametocytes at admission up to day 14, stratified by the presence of gametocytes at enrolment

- Correlation between the host genotype (e.g., CYP2D6, CYP3A4, KCNQ1/LQT1, KCNH2/LQT2, SCN5A/LQT3) and the pharmacokinetics and pharmacodynamics of antimalarials.
- Correlations between the place of residence, work, recent travel history assessed by interview and mobile phone records to identify behaviours and risk factors associated with malaria infection.
- Correlation between specific antibody titres and measures of drug efficacy

6. TRIAL DESIGN

6.1. Study sites

The study will take place in up to 8 sites in 8 countries (provisional list in Appendix 3). Estimated total sample size is 3240 subjects.

6.2. Summary of trial design

A partially blinded randomised controlled non-inferiority trial of the Triple ACTs artemether-lumefantrine + amodiaquine (AL+AQ) and artesunate-mefloquine + piperazine (ASMQ+PPQ) with the ACTs artemether-lumefantrine + placebo (AL+PBO) and artesunate-mefloquine + placebo (ASMQ+PBO) for the treatment of uncomplicated *Plasmodium falciparum* malaria to assess and compare their efficacy, safety, tolerability. (See sub-section 9.4 for further details regarding partial blinding).

6.3. Study duration

Projected recruitment duration of 21 months September 2020 – June 2022; study projected to finish in March 2023.

7. PROPOSED ACTIVITIES

Subjects will be randomized to up to four arms: artemether-lumefantrine + amodiaquine, artemether-lumefantrine + placebo, artesunate-mefloquine + piperazine and artesunate-mefloquine + placebo. As a contingency measure in case of significant differences in the efficacy or safety of one of the combinations being tested and/or study drug expiry or unavailability, subjects may be randomized to 2 arms with a matching ACT-TACT pair, i.e., with artemether-lumefantrine + placebo or artemether-lumefantrine + amodiaquine OR artesunate-mefloquine + placebo or artesunate-mefloquine + piperazine.

Some sites may randomize between 2 arms only with matching ACT-TACT pairs, i.e., artemether-lumefantrine + placebo or artemether-lumefantrine + amodiaquine OR artesunate-mefloquine + placebo or artesunate-mefloquine + piperazine. In Rwanda, subjects will be randomized between 2 arms consisting of artemether-lumefantrine + placebo or artemether-lumefantrine + amodiaquine.

In the control arms, the ACT will be co-packed with a matched (appearance) placebo.

In lower transmission settings (Annual Parasite Incidence <50 per 1000 population per year) the treatment will include a single 0.25 mg/kg gametocytocidal dose of primaquine as recommended by the WHO for children ≥ 10 kg. All drug administrations will be observed.

Subjects will be treated in an in-patient unit for 3 days and followed up weekly up to D63. Microscopy to detect and quantify malaria parasitaemia will be performed daily (more frequently in patients with parasite density of $>5000/\mu\text{L}$ at inclusion) during hospitalization, at all weekly and unscheduled visits. A physical examination and measurements of vital signs along with a symptom questionnaire for tolerability will be performed and recorded through a standardized method at baseline, daily during admission and weekly during follow up through D42 and at all unscheduled visits. Physical exam, vital sign measurements and assessments of symptoms will be performed on D49, D56, and D63 only for patients who are parasitaemic or those who report fever or other symptoms. Electrocardiographs will be performed during admission (H0, H4, H52 or H64) and day 42 of follow up to assess and compare the effect of ACTs and TACTs antimalarials on QT or QTc intervals.

Safety assessments will be performed by measuring markers of renal and hepatic toxicity, haemoglobin, platelet counts, absolute and differential white blood cell counts and ECGs. Pharmacokinetic profiles in a subset of subjects will be linked to measures of efficacy and toxicity. To avoid extensive blood sampling, especially in children, a population pharmacokinetic approach will be followed, requiring sparse blood sampling reducing the burden of sampling for the patient [21].

Blood samples for parasite genotyping as well as genomic, transcriptomic and immunology studies will be collected at baseline and at selected time-points on follow-up and also on the day of a recurrent infection.

In patients with parasite densities >5000 per μL at screening, parasite clearance rates will be assessed by repeated assessments of the parasite counts after the start of the antimalarial treatments in approximately 250 patients. At each visit a capillary blood sample will be taken for parasite count.

If a patient presents with a new uncomplicated falciparum malaria infection after 3 months or longer after the initial enrolment, the patient or relative (in case of a child) will be asked to re-enter the patient in the trial.

In selected study sites, *P. falciparum* parasites will be cryopreserved for *in vitro* antimalarial drug sensitivity testing. Where possible, *ex vivo* or *in vitro* assessments of parasite susceptibility to artemisinins and partner drugs will be assessed.

The *in vivo* and *ex vivo* data on artemisinin and partner drug sensitivity will potentially be used to identify new genetic or transcriptomic markers/patterns of artemisinin or partner drug resistance.

The pharmacogenetics of antimalarial agents are poorly known despite the fact that application of pharmacogenetics might be critical in optimizing treatment of malaria in individuals but also populations at large. Blood samples (dried blood blots) for human genotyping will be obtained and stored from all subjects recruited with subject's consent.

Subjects or their guardians will be asked a short set of questions on their place of residence, place of work and their history of travel in the last 2 months. In addition, basic questions on use of mobile phones will be asked. These questions will help in understanding the use of mobile phones in each country in subjects prone to malaria infections which can inform future malaria studies or interventions.

All the organisations in this collaboration will work closely with local counterparts including the National Malaria Control Programmes (NMCPs), non-governmental and other relevant organisations. Training is an integral part of this collaborative working relationship, and the building of local research capacity is an essential component of all research plans.

All research-related activities, from study design, planning, implementation through to analysis and writing of reports will be performed jointly with local counterparts. Both on-the-job training and formal training will be provided when needed, in particular for Good Clinical Practice (GCP) skills.

The close interaction between WHO and its regional offices will ensure that new knowledge is disseminated efficiently and effectively throughout the region. The Worldwide Antimalarial Resistance Network website (www.wwarn.org) will be also used as a medium to disseminate information.

8. TRIAL PARTICIPANTS

8.1. Overall description of trial participants

African sites: Male and pre-menarchal female subjects aged ≥ 6 months to < 12 years (For Gambia, Rwanda sites only: ≥ 6 months; female subjects who are not pregnant nor trying to get pregnant and who are not lactating will also be included) with acute uncomplicated falciparum malaria are the target study population. All study subjects must meet the applicable inclusion and exclusion criteria.

8.2. Inclusion criteria

- Male or female, aged ≥ 6 months to < 12 years (For Gambia, Rwanda sites only: ≥ 6 months)
- Ability to take oral medication
- Acute uncomplicated *P. falciparum* mono-infection
- Asexual *P. falciparum* parasitaemia: 1,000/ μ L to $\leq 10\%$ parasitaemia, determined on a peripheral blood film (For Gambia, Rwanda sites only: For subjects ≥ 12 years – 1000/ μ L to 200,000/ μ L)
- Fever defined as $> 37.5^{\circ}\text{C}$ tympanic temperature or a history of fever within the last 24 hours
- Written informed consent by the subject or by parent/guardian in case of children lower than the age of consent and assent if required (per local regulations)
- Willingness and ability of the subjects or parents/guardians to comply with the study protocol for the duration of the study

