8.3. Exclusion criteria

- Signs of severe malaria (adapted from WHO criteria, see section 8.4)
- Patients not fulfilling criteria for severe malaria but with another indication for parenteral antimalarial treatment at the discretion of the treating physician
- Haematocrit <15% at screening (For Gambia, Rwanda sites only: For subjects ≥12 years – Haematocrit <20% at screening)
- Subjects who have received artemisinin or a derivative within the previous 7 days OR lumefantrine or amodiaquine within the previous 14 days OR mefloquine or piperaquine within the previous 30 days
- In applicable countries: use of seasonal malaria chemoprophylaxis (SMC) within the last 14 days.
- Acute illness other than malaria requiring systemic treatment
- Severe acute malnutrition (in Niger – only those patients with Severe Acute Malnutrition and complications requiring inpatient nutritional treatment will be excluded)
- Known HIV infection
- Known tuberculosis infection
- For females: post-menarche (For Gambia, Rwanda sites only: females who are pregnant, trying to get pregnant or are lactating)
- History of allergy or known contraindication to any of the study drugs, including neuropsychiatric disorders and epilepsy
- Previous splenectomy
- Enrolment in DeTACT in the previous 3 months
- Participation in another interventional study in the previous 3 months

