9.10. Blood volumes

The blood volumes for the protocol mandated tests are detailed in the study schedule (Appendix 1) and will vary slightly between sites depending on whether sites can perform all of the tests of this protocol e.g. not all sites will be able to do the full blood count, store the plasma PK samples or do the *ex vivo* parasite culture. Also, it is likely that only a minority of subjects will develop a recurrent parasitaemia and be requested to give further blood samples.

Concerning blood volumes, an age of 12 years and older will be referred to as 'adult', an age of less than 12 years will be referred to as 'child'.

Maximum blood volumes are presented below for 63 days of follow up. The maximum blood volume is the total amount taken if the subjects remained in hospital for 3 days, had all blood samples taken and where part of the pharmacokinetic as well as other subsets (like qPCR validation and sampling for gametocyte genetics) and had one recurrent parasitaemia and/or unscheduled visit during follow up. The maximum blood volume will be approximately **48.5 ml (66.5 mL** in subjects ≥ 12 years in Gambia, Rwanda only), which is less than 10% of total blood volume generally recommended as a maximum volume to be taken over 8 weeks.. At the Niger site ONLY, where an additional 1 mL sample will be collected within a random time window between D0 & D7, the maximum blood volume will be approximately **49.5 mL**.

The maximum blood volume that will be drawn in children below the age of 12 is **17.5 ml** in the first 24 hours of the study. This is below the 3 ml/kg in the first 24 hours as recommended only if

the subjects are ≥ 6 kg [25]. Accordingly, samples collected from children of <6 kg will only be those which are specifically required for the efficacy, safety and tolerability assessments, viz., blood smears, dried blood spots, venous samples for clinical biochemistry, haematology and PK samples.

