10. STUDY DRUG

10.1. Study drug regimens

Overview DeTACT drug regimens	
TACT-arm	ACT-arm
In all sites	
Artemether -lumefantrine x 3 days PLUS Amodiaquine x 3 days	Artemether -lumefantrine x 3 days PLUS Placebo x 3 days
In all sites except Rwanda	
Artesunate -mefloquine x 3 days PLUS Piperaquine x 3 days	Artesunate -mefloquine x 3 days PLUS Placebo x 3 days
In low transmission settings subjects will receive a single low dose primaquine on day 1 according to the WHO guidelines and local regulations	

Subjects will be treated with weight-based doses according to the schedule in appendix 2.

The study drugs will be administered by study medical or nursing staff while the subjects are hospitalised.

The study drugs containing artemether-lumefantrine+/-placebo will be taken with at least 1.2 grams of fat to optimize absorption (comparable to 80-100 ml of a MILO milk carton or an equivalent fat containing beverage or snack).

No meals or snacks must be consumed for 1 hour before and after intake of study drugs containing artesunate-mefloquine+/-piperaquine. In case any food is taken, it must be non-fatty snacks (e.g., small quantity of rice, bread, crackers, etc.)

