10.6.1. Artemether-lumefantrine

Currently available as dispersible tablets containing 20 mg of artemether and 120 mg of lumefantrine, in a fixed-dose combination formulation. The flavoured dispersible tablet paediatric formulation facilitates use in young children.

Target dose/range:

The dose of artemether-lumefantrine is administered according to the treatment schedule in appendix 2, thereby approaching the WHO-recommended target ranges of artemether 5-24 mg/kg and lumefantrine 29-144 mg/kg over 3 days.

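### Eligibility sets no body-weight criterion, but every dosing table for the two study regimens starts at 5 kg, so an eligible child below 5 kg has no protocol dose

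*Protocol*

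**What the plan says.** The lower entry condition is age. Section 8.2 reads "Male or female, aged ≥ 6 months to < 12 years (For Gambia, Rwanda sites only: ≥ 6 months" (the open-ended age range applies at those two sites), and the synopsis has the same rule. No inclusion bullet names a body weight. The nearest is "Ability to take oral medication".

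Section 8.3 and the synopsis name no body weight among the exclusions either. Severe acute malnutrition is excluded generally, but with a carve-out: "in Niger – only those patients with Severe Acute Malnutrition and complications requiring inpatient nutritional treatment will be excluded". The only other exclusion that might act indirectly is "History of allergy or known contraindication to any of the study drugs, including neuropsychiatric disorders and epilepsy".

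Dosing depends entirely on weight. Section 10.1 states: "Subjects will be treated with weight-based doses according to the schedule in appendix 2". Appendix 2 has four tables for the two study regimens, one in milligrams and one in tablets for each. Both AL+/-AQ tables begin with the band 5 to 9.9 kg, and both ASMQ+/-PPQ tables with 5 to 10.9 kg. No row, footnote or section text covers a lower weight.

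Section 9.10 does address very small children, but only for blood volume: "samples collected from children of <6 kg will only be those" needed for the efficacy, safety and tolerability assessments.

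**The concern.** Eligibility and dosing use different variables, and their lower ends are not tied together. A child aged 6 months or more who weighs less than 5 kg satisfies the entry criteria, yet Appendix 2 has no row from which to treat that child in any arm.

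At stake is the treatment of an individual child with acute malaria. A site following the plan would have to use a row that does not apply, improvise a dose, or turn away or stop a child whom the protocol calls eligible. Sites could resolve this differently, and nothing in the protocol tells them which course to take.

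**Working it through.** **Step 1. Is there a weight condition anywhere in eligibility?** None appears in the inclusion or exclusion lists of sections 8.2 and 8.3, or in the synopsis versions. Ability to take oral medication is not a weight limit, and the contraindication exclusion names no weight. Where the sponsor wanted a weight rule it wrote one: primaquine is withheld below 10 kg (synopsis and section 7). That rule concerns an add-on drug and does not affect entry to the trial.

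**Step 2. Does the lowest row tacitly cover smaller children?** Inputs from Appendix 2, lowest band:
- Artemether 20 mg and lumefantrine 120 mg per dose, six doses over 3 days.
- Amodiaquine 40 mg per dose, two doses per day.
- Piperaquine 160 mg once daily.

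Stated ranges:
- Section 10.6.1: the "WHO-recommended target ranges of artemether 5-24 mg/kg and lumefantrine 29-144 mg/kg over 3 days".
- Section 10.6.2: amodiaquine 4.5 to 15 mg/kg/day.
- Section 10.6.5: piperaquine 16.0 to 32.0 mg/kg/day below 25 kg.

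Formula: dose per kg = (tablet content × number of doses) / body weight. At exactly 5.0 kg:
- Artemether: 6 × 20 / 5 = 24 mg/kg over 3 days (stated upper end 24).
- Lumefantrine: 6 × 120 / 5 = 144 mg/kg over 3 days (stated upper end 144).
- Piperaquine: 160 / 5 = 32 mg/kg/day (stated upper end 32.0).
- Amodiaquine: 2 × 40 / 5 = 16 mg/kg/day (stated upper end 15).

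Three of the protocol's own upper figures are reproduced exactly by a 5.0 kg child. The stated ranges therefore match a 5 kg floor that the eligibility criteria do not impose. The fourth figure is already exceeded at that weight. For artesunate and mefloquine, sections 10.6.3 and 10.6.4 give a single target and no range, so the same comparison cannot be made.

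**Step 3. What would carrying the row downward do?** The protocol authorises no such practice, and the weights below are assumed only to show the direction.
- At 4.5 kg: artemether 120 / 4.5 = 26.7, lumefantrine 720 / 4.5 = 160, piperaquine 160 / 4.5 = 35.6. Each is 5 / 4.5 = 1.11 times the upper figure.
- At 4.0 kg: 30, 180 and 40. Each is 5 / 4 = 1.25 times the upper figure.

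**Step 4. Does the under-6-kg rule in section 9.10 help either way?** The first-24-hour volumes in Appendix 1 are 0.5 + 10 + 2.5 + 1.5 + 0.5 + 2.5 = 17.5 mL, as section 9.10 states. Dividing by the 3 mL/kg guide gives 17.5 / 3 = 5.83 kg, which explains the 6 kg threshold. It is a blood-volume rule, and it neither sets a minimum weight for entry nor supplies a dose.

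**Step 5. When would the site find out?** Appendix 1 marks height and weight at screening as well as at hour 0, although the extracted table is broken. Randomisation is marked at hour 0. The information needed to detect the mismatch is thus available before allocation.

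**The case against.** The best case on the other side accepts the gap in the text and disputes its reach.

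- **Frequency.** The documents give no weight distribution. If children this small are mostly severely malnourished, the general exclusion already removes most of them at seven of the eight sites. At Niger (432 of 3240 planned subjects) complicated cases and children unable to take oral medicine are still excluded. This stands. That Niger is where the gap would arise is plausible, but it is an inference.
- **Ranges are not caps.** A reader might infer that using the lowest row below 5 kg would break dose limits. The documents do not support that: section 10.6.1 speaks of approaching target ranges, and sections 10.6.2 and 10.6.5 of approximate aims. The tables themselves stray outside the ranges elsewhere. Piperaquine at 10.9 kg is 160 / 10.9 = 14.7 mg/kg/day against a lower figure of 16.0, and at 33.9 kg it is 500 / 33.9 = 14.7 against 15.0. The ranges show only that the lowest row cannot be presumed to extend downward.
- **Section 9.10.** A reader might take the under-6-kg rule as evidence that children below 5 kg are expected. It is equally met by children of 5.0 to 5.9 kg, who have a dose row, so it proves nothing here.
- **Site behaviour.** A careful site would see that no row applies and could contact the study team before opening an envelope. That is likely, but the protocol does not say so. The contraindication exclusion might be invoked, but it names no weight and so does not close the gap.
- **Trial integrity.** A reader might fear damage to the intention-to-treat analysis. One or a few untreated randomised children are negligible against the 20% allowance for loss to follow-up, and the gap affects both regimens alike.

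None of these points supplies the missing dose row or the missing criterion.

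**Conclusion.** The contradiction is real. Sections 8.2 and 8.3 and the synopsis allow a child under 5 kg to be randomised, while section 10.1 and Appendix 2 give that child no dose in any arm. It is a conflict between two operative parts of the protocol that bears on patient safety, and it should be corrected.

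Its size is undocumented and probably very small. The conclusion rests on the texts alone and needs no assumption about how many such children exist or where. It does not depend on the target ranges being limits, on section 9.10, or on any effect on the efficacy analysis.

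**What to change.** The sponsor should reconcile the eligibility criteria (sections 8.2 and 8.3 and the synopsis) with the Appendix 2 tables, so that the set of children who can be randomised and the set with a dose row are the same. The match should be checked on the screening weight before randomisation. Whether the eligibility text or the appendix changes, and how, is the sponsor's decision; no dose or weight threshold is proposed here. In the same pass, the amodiaquine figure at 5 kg (16 against 15 mg/kg/day) should be reconciled with section 10.6.2.

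The textual cost is small: a short clarification in the next amendment and one check on the screening form, using a weight that Appendix 1 already schedules. Any clinical work behind the decision depends on which text the sponsor changes.
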